#### 4.2.1.3 Dose Modification Guidelines for Lenalidomide

Dose modification guidelines are based on the recommendation provided by the Myeloma expert panel review[58] of the efficacy and toxicity of lenalidomide plus dexamethasone, and the guidance provided in the product label for lenalidomide. Any toxicity associated with lenalidomide that prompts a dose reduction of lenalidomide is outlined in the Sections below.

Lenalidomide is administered once daily from Day 1 through Day 14 in each 21 day cycle. If a subject receiving 5 mg of lenalidomide experiences an AE related to lenalidomide and is in need of dose modification, the subject should discontinue lenalidomide and continue only pembrolizumab (MK-3475) and dexamethasone, as 5 mg is the lowest dose used in

Pembrolizumab (MK-3475), [name], HUMC

this trial. A maximum of three dose reductions of lenalidomide will be allowed in the order indicated in Table 6, where applicable. The duration of administration will remain the same.

A subject cannot be restarted on lenalidomide unless non-hematologic lenalidomide-related toxicities have returned to at least Grade 1 toxicity or baseline.

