However, a more recent Phase III randomized study (known as E4A03) sponsored by the US National Cancer Institute (NCI), and conducted by a network of researchers led by the Eastern Cooperative Oncology Group (ECOG) compared combination treatment of lenalidomide and either high- or low-dose dexamethasone in 445 patients with myeloma[55]. The dose of dexamethasone considered "low-dose" in this trial was 40 mg on Days 1, 8, 15, and 22 (i.e. once weekly) in each 28-day cycle. Researchers found that patients in the study who received low-dose dexamethasone and lenalidomide had a one-year survival of 96 percent compared to 86 percent for patients treated with the standard or high -dose of dexamethasone and lenalidomide[56]. In addition, there were fewer side effects associated with the low-dose dexamethasone and lenalidomide. Based on this study, there is evidence that lowering the dexamethasone dose may reduce side effects and improve survival. The National Comprehensive Cancer Network (NCCN) MM guidelines also list

the lenalidomide, low dose-dexamethasone combination as an initial therapy for non-transplant candidates. There is an ongoing Phase I trial to establish the safety and the RP2D of pembrolizumab (MK-3475) in combination with lenalidomide and low-dose dexamethasone in subjects with relapsed/refractory MM who have failed at least two lines of prior therapy, including a proteasome inhibitor (e.g. bortezomib or carfilzomib) and an IMiD (thalidomide, pomalidomide, lenalidomide).

Biologically, this Phase 2 pilot study allows the combination of pembrolizumab, lenalidomide and dexamethasone to provide maximal cytoreduction post-ASCT for the first two cycles of therapy. And subsequently, the discontinuation of dexamethasone for the following 2 cycles will allow for maximization of potential long-term immunological benefits seen with pembrolizumab combined with lenalidomide alone.

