## 4.2 Trial Treatments

Trial treatment should be administered starting with Day 1 of the first 28-day cycle after all procedures/assessments have been completed as detailed on the Trial Flow Chart (Section 5.0). Trial treatment may be administered up to 3 days before or after the scheduled day of administration due to administrative reasons. The treatment(s) to be used in this trial are outlined below in Table 2.

Table 2 Trial Treatments

Dose		
Pembrolizumab (MK-3475)	Lenalidomide	Dexamethasone
200 mg	25 mg	40 mg*

Pembrolizumab (MK-3475) will be administered every 3 weeks (on Day 1 of each 21-day cycle).  
Lenalidomide will be dosed on Days 1-14 of each 21-day cycle.  
Dexamethasone will be dosed on Days 1,8, and 15 of each 21-day cycle for the first 2 cycles only.  
\* A dexamethasone dose of 20 mg on Days 1,8, and 15 of each 21-day cycle is recommend for **subjects aged >75**.

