### **Dexamethasone**

The recommended dose of dexamethasone is 40 mg once weekly on Days 1, 8, and 15 of each 21-day cycle. A dexamethasone dose of 20 mg once weekly on Days 1, 8, and 15, in subjects aged **>75 years** is recommended. Refer to local product label for more details. Patients to receive dexamethasone in the first 2 cycles only.

The investigator shall take responsibility for and shall take all steps to maintain appropriate records and ensure appropriate supply, storage, handling, distribution and usage of trial treatments in accordance with the protocol and any applicable laws and regulations.

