#### 4.2.1.3.2 Other Grade 3/4 Toxicities in MM

For other Grade 3/4 toxicities, hold treatment and restart at the physician's discretion at next lower dose level when toxicity has resolved to  $\leq$  Grade 2 as outlined below in [Table 6](#).

Table 6 Lenalidomide Dose Reductions for Subjects with Other Grade 3/4 Toxicities

Modification	Dose 
Starting Dose	Lenalidomide 25 mg every day for 14 days, every 21 days
Dose Reduction 1	Lenalidomide 15 mg every day for 14 days, every 21 days
Dose Reduction 2	Lenalidomide 10 mg every day for 14 days, every 21 days
Dose Reduction 3	Lenalidomide 5 mg every day for 14 days, every 21 days
 Do not dose below 5 mg daily	
 If the subject is receiving Len 10 mg, the subject may resume Len at 5 mg.	

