#### **4.5.2 Prohibited Concomitant Medications**

Subjects are prohibited from receiving the following therapies during the Screening and Treatment Phase (including retreatment for post-complete response relapse) of this trial:

- Antineoplastic systemic chemotherapy or biological therapy
- Immunotherapy not specified in this protocol
- Chemotherapy not specified in this protocol
- Investigational agents other than pembrolizumab
- Radiation therapy
  - Note: Radiation therapy to a symptomatic solitary lesion or to the brain may be allowed at the investigator's discretion.
- Live vaccines within 30 days prior to the first dose of trial treatment and while participating in the trial. Examples of live vaccines include, but are not limited to, the following: measles, mumps, rubella, varicella/zoster, yellow fever, rabies, BCG, and typhoid vaccine.
- Systemic glucocorticoids for any purpose other than to modulate symptoms from an event of clinical interest of suspected immunologic etiology. The use of physiologic doses of corticosteroids may be approved after consultation with the Sponsor.

Subjects who, in the assessment by the investigator, require the use of any of the aforementioned treatments for clinical management should be removed from the trial. Subjects may receive other medications that the investigator deems to be medically necessary.

The Exclusion Criteria describes other medications which are prohibited in this trial.

There are no prohibited therapies during the Post-Treatment Follow-up Phase.

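### The lenalidomide stop rule tells sites to continue dexamethasone, but it would normally be reached in cycle 3 or 4, when no dexamethasone is scheduled

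*Combined protocol and SAP*

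**What the plan says.** Section 4.2.1.3 sets the trigger: "If a subject receiving 5 mg of lenalidomide experiences an AE related to lenalidomide and is in need of dose modification". It then gives the instruction: "the subject should discontinue lenalidomide and continue only pembrolizumab (MK-3475) and dexamethasone". Neither sentence mentions a cycle. The same section caps the step-downs: "A maximum of three dose reductions of lenalidomide will be allowed".

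The treatment schedule limits dexamethasone. The note to Table 2 in section 4.2 reads "Dexamethasone will be dosed on Days 1,8, and 15 of each 21-day cycle for the first 2 cycles only", and the dexamethasone paragraph repeats it: "Patients to receive dexamethasone in the first 2 cycles only". Section 1.1 and the trial summary describe cycles 3 and 4 as pembrolizumab with lenalidomide, without dexamethasone. Section 3.2.1.4 gives the reason: "the discontinuation of dexamethasone for the following 2 cycles will allow for maximization of potential long-term immunological benefits".

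Two other places bear on the point. Section 4.2.1.4, on dexamethasone dose changes, describes weekly dosing in every 21-day cycle and does not repeat the two-cycle limit. Section 4.5.2 prohibits, during screening and treatment, "Systemic glucocorticoids for any purpose other than to modulate symptoms from an event of clinical interest of suspected immunologic etiology", and does not exempt the protocol's own dexamethasone.

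**The concern.** An instruction to continue a drug can be carried out only while that drug is being given. In cycles 3 and 4 the schedule contains no dexamethasone. A site applying section 4.2.1.3 there must either give dexamethasone outside the schedule in sections 1.1 and 4.2, or give pembrolizumab alone and depart from the words of section 4.2.1.3. Staff working only from the dose-modification sections would not meet the two-cycle limit at all.

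At stake is what a subject receives after repeated lenalidomide toxicity, and whether two subjects in the same position are treated alike. How much this matters depends on when in the four cycles the rule can be reached, and on how much treatment remains at that point.

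**Working it through.** **Inputs from the protocol.** Four 21-day cycles (1.1). Lenalidomide on Days 1-14 and pembrolizumab on Day 1 of each cycle; dexamethasone on Days 1, 8 and 15 of cycles 1-2 (4.2). At most three lenalidomide reductions (4.2.1.3). Table 6 starts at "Lenalidomide 25 mg every day for 14 days, every 21 days" and steps down to 15, 10 and 5 mg (4.2.1.3.2). Weekly blood counts during a haematological hold (Tables 4 and 5).

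**Step 1: reproduce the stated maximum.** Table 6 lists four dose levels, and 4 - 1 = 3 reductions, which agrees with section 4.2.1.3. The stop needs one toxicity at each level, so four episodes. The platelet path (Table 4) and the branch of Table 5 with another toxicity also run 25, 15, 10, 5 mg. The neutropenia-only branch of Table 5, read literally, runs 25, 25, 20, 15, 10, 5 mg and needs six episodes. At one per cycle, six do not fit into four cycles.

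**Step 2: one episode per cycle.** The doses are 25 mg in cycle 1, 15 mg in cycle 2, 10 mg in cycle 3 and 5 mg in cycle 4. Cycle 4 starts on Day 3 × 21 + 1 = 64, and its lenalidomide days are 64-77. The fourth episode therefore falls on Days 64-77. Restart allowed only on the next Day 1 gives the same result.

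**Step 3: mid-cycle restart.** No section forbids restarting within a cycle or reducing more than once per cycle. Assume that each episode occurs on the t-th dosing day at that level, is followed by a hold of h calendar days, and that dosing resumes on the first lenalidomide day after the hold. Counting forward from Day 1 on nominal cycle dates gives the study day (and cycle) of the fourth episode:

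| t (dosing days) | h = 1 | h = 3 | h = 5 | h = 7 | h = 10 | h = 14 |
|---|---|---|---|---|---|---|
| 1 | 7 (C1) | 13 (C1) | 22 (C2) | 30 (C2) | 34 (C2) | 64 (C4) |
| 3 | 22 (C2) | 28 (C2) | 32 (C2) | 34 (C2) | 56 (C3) | 66 (C4) |
| 4 | 25 (C2) | 32 (C2) | 34 (C2) | 46 (C3) | 67 (C4) | 67 (C4) |
| 6 | 34 (C2) | 47 (C3) | 48 (C3) | 66 (C4) | 69 (C4) | 69 (C4) |
| 7 | 45 (C3) | 49 (C3) | 64 (C4) | 70 (C4) | 70 (C4) | 70 (C4) |
| 10 | 64 (C4) | 70 (C4) | 73 (C4) | 73 (C4) | 73 (C4) | not reached |
| 14 | 77 (C4) | 77 (C4) | 77 (C4) | 77 (C4) | not reached | not reached |

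As an example, take t = 7 and h = 7. Episodes fall on Days 7, 28, 49 and 70. Each hold runs to the end of that cycle's dosing days, so dosing resumes on Days 22, 43 and 64.

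With seven or more dosing days per episode, the stop is in cycle 3 or 4, or is never reached, at every hold tested. With a 7-day hold, a stop within cycles 1-2 needs toxicity after three or fewer dosing days each time.

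**Step 4: what treatment is left.** Pembrolizumab is due on Days 1, 22, 43 and 64.
- Stop in cycle 4: the last infusion is already due on Day 64. If dexamethasone were given in that cycle it would fall on Days 64, 71 and 78, so at most two days (71 and 78) are in question.
- Stop in cycle 3, after Day 43: one infusion (Day 64) remains. At most five weekly dexamethasone days are in question (50, 57, 64, 71 and 78).

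**The case against.** The strongest reply is that the word continue presupposes an ongoing drug. On that reading section 4.2.1.3 orders nobody to restart dexamethasone. It fits the schedule in cycles 1-2 and is merely loose afterwards. This is a fair reading and probably the one many sites would adopt. It does not settle the matter, because the sentence names dexamethasone without qualification and no section says how it applies once dexamethasone has ended.

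The timing in the working is also an inference. Cycle 2, or even cycle 1, is possible with very rapid repeat toxicity. That stands, and it is why the point is limited to when the rule would normally be reached.

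A reader might infer three larger consequences that the documents do not support:

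- **Removal from the trial.** Section 4.5.2 says subjects needing a prohibited treatment should be removed, so giving dexamethasone in cycle 3 or 4 might seem to trigger removal. Read that literally, however, the same line would also bar the scheduled dexamethasone of cycles 1-2. The missing exemption is a separate drafting gap that touches every subject. It is not a removal route created by the stop rule.
- **Loss of disease follow-up.** Sections 1.1, 4.8 and 6.1.4.5 already follow subjects who discontinue for reasons other than progression. Section 7.1.7.1 analyses PFS in all enrolled subjects.
- **Compromised correlative samples.** No section requires these samples to be steroid-free. Section 3.2.1.4 speaks of benefit from treatment, not of sampling conditions. Marrow is scheduled at screening and after cycle 4, and the analyses are exploratory.

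**Conclusion.** The inconsistency is real and rests on the text alone. Section 4.2.1.3 tells a subject who stops lenalidomide to continue a drug that sections 1.1 and 4.2 have by then withdrawn, in the cycles where the rule would normally apply.

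Its size is small. Four lenalidomide-related episodes within twelve weeks are needed. The documents give no rate, so the number of affected subjects among the planned 43 cannot be estimated and may be zero. At one step-down per cycle, no pembrolizumab infusion remains and at most two dexamethasone days are open. Faster repeat toxicity that puts the stop in cycle 3 leaves one infusion and at most five dexamethasone days open. These counts assume nominal cycle dates and the episode and hold lengths shown.

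Sample size, type I error, disease follow-up and the primary analysis are not affected. This is an inconsistency of wording in a treatment rule, worth correcting because sites should not have to choose between sections after repeated toxicity.

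**What to change.** Reconcile section 4.2.1.3 with sections 1.1, 3.2.1.4 and 4.2. State separately for cycles 1-2 and for cycles 3-4 what a subject who permanently stops lenalidomide continues to receive. Carry the same cycle limits into section 4.2.1.4 so that the dose-modification text can be used on its own. Align the glucocorticoid item in section 4.5.2 with whatever protocol dexamethasone is intended. Which treatment continues in each period is a clinical decision for the sponsor, and this review does not propose one.

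The cost is one or two sentences in section 4.2.1.3, with matching clauses in sections 4.2.1.4 and 4.5.2. No procedures, visits or subjects are added, and the statistical section needs no change.

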#### **4.2.1.3.1 Dose Adjustments for Hematologic Toxicities during Multiple Myeloma Treatment**

Dose modification guidelines, as summarized below in [Table 4](#) and [Table 5](#), are recommended to manage Grade 3 or 4 neutropenia or thrombocytopenia or other Grade 3 or 4 toxicities judged to be related to lenalidomide. Please refer to local product label for additional guidelines.

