#### 4.2.1.3.3 Recommended Dose Adjustments for Subjects with Impaired Renal Function

Renal function may be impaired in subjects with MM by immunoglobulin light chains, amyloidosis. MM subjects with normal renal function may develop renal dysfunction or renal impairment during treatment with lenalidomide and dexamethasone. If renal toxicity occurs during study treatment, drug should not be restarted unless the toxicity resolved to  $\leq$  Grade 1.

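### Lenalidomide restart: Sections 4.2.1.3 and 4.2.1.3.2 set different recovery grades, and they conflict for some non-haematologic, non-renal Grade 3/4 events that have improved to Grade 2

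*Combined protocol and SAP*

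**What the plan says.** Three places in the protocol's lenalidomide guidance govern restart after toxicity.

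- **Section 4.2.1.3, general rule:** "A subject cannot be restarted on lenalidomide unless non-hematologic lenalidomide-related toxicities have returned to at least Grade 1 toxicity or baseline". The natural reading is Grade 1 or better, or the patient's own baseline. The same section says that a patient on 5 mg who needs a modification stops lenalidomide. It also refers to the reduction ladder: "A maximum of three dose reductions of lenalidomide will be allowed in the order indicated in Table 6, where applicable".
- **Section 4.2.1.3.2, other Grade 3/4 toxicities:** "For other Grade 3/4 toxicities, hold treatment and restart at the physician's discretion at next lower dose level when toxicity has resolved to" a stated grade, which appears in the words "toxicity has resolved to $\leq$ Grade 2". The ladder it points to is Table 6, titled "Lenalidomide Dose Reductions for Subjects with Other Grade 3/4 Toxicities".
- **Section 4.2.1.3.3, renal impairment:** after renal toxicity on study, "drug should not be restarted unless the toxicity resolved to" Grade 1 or lower. It does not mention return to baseline, and it does not say which drug is meant.

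Section 4.2.1.3.1 introduces the tables and describes the remaining class as "other Grade 3 or 4 toxicities judged to be related to lenalidomide".

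**The concern.** A general rule that forbids restart above a given grade and a subsection that permits it at a higher grade cannot both guide the same decision. An investigator who relies on 4.2.1.3.2 and restarts at Grade 2 acts within that paragraph. A monitor who reads 4.2.1.3 would record the same act as a deviation.

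The decision bears on safety, because it determines when a patient is re-exposed after a severe event. It also bears on how conduct is judged. Noncompliance with trial treatment is a ground for discontinuing a subject (Section 4.8), and poor adherence to the protocol is a ground for ending the trial (Section 4.9). Protocol violations are to be identified before the database is final (Section 7.1.4). None of these can be applied consistently while one restart can be both compliant and a violation.

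**Working it through.** The plan gives no figure to reproduce, and the point depends on no sample size, power or event count. The check compares the scope and the threshold of the two rules.

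**Step 1: do both rules govern lenalidomide?** Yes. Section 4.2.1.3 names the drug. Section 4.2.1.3.2 says only that treatment is held, but it sends the reader to Table 6, which is a lenalidomide table. Section 4.2.1.3 sends the reader to the same table.

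**Step 2: do the scopes overlap?** Section 4.2.1.3 covers non-haematologic, lenalidomide-related toxicity. Section 4.2.1.3.2 covers Grade 3/4 toxicities other than those in Tables 4 and 5, which deal with platelets and neutrophils. Section 4.2.1.3.1 describes that remaining class as related to lenalidomide. A non-haematologic, lenalidomide-related Grade 3/4 event therefore falls under both.

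**Step 3: compare the answers by state of recovery.** Take a non-haematologic, non-renal, lenalidomide-related Grade 3/4 event in a patient above 5 mg.

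| State after the hold | Section 4.2.1.3 | Section 4.2.1.3.2 | Conflict? |
|---|---|---|---|
| Grade 0–1 | Restart not barred | Restart permitted | No |
| Grade 2, baseline Grade 2 | Restart not barred (back to baseline) | Restart permitted | No |
| Grade 2, baseline below Grade 2 | Restart barred | Restart permitted at the physician's discretion | **Yes** |
| Grade 3–4 | Restart barred, unless that was the baseline grade | Restart not permitted | No, except in that unusual baseline case |

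**Step 4: remove what lies outside the conflict.**

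- Haematologic events: the sentence in 4.2.1.3 does not reach them.
- Renal events: 4.2.1.3.3 sets its own limit at Grade 1 or lower.
- Patients already on 5 mg who need a modification: they stop lenalidomide under 4.2.1.3, so no restart arises.

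**Step 5: look for a rule of precedence.** None was found. Table 3a concerns pembrolizumab. The local product label is cited for further guidance, but the protocol does not say that it overrides either sentence.

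**Step 6: the renal paragraph.** Its Grade 1 limit matches that of 4.2.1.3. The difference is the missing return to baseline: a patient whose baseline renal grade was above 1 could meet 4.2.1.3 and fail 4.2.1.3.3.

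**Scale for one patient (illustration only).** Lenalidomide is planned for 14 days in each of 4 cycles, so 4 × 14 = 56 dosing days. If waiting for the lower grade cost exactly one full cycle of dosing, that would be 14 / 56 = 25% of planned lenalidomide days. If recovery to Grade 1 came within the 7 drug-free days of the cycle (21 − 14 = 7), before the next planned dose, the cost would be 0. The documents give no basis for placing a patient within that range.

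**The case against.** **The rules can be obeyed together.** Section 4.2.1.3.2 is permissive and 4.2.1.3 is a prohibition, so a physician who waits breaches neither. This is correct, and it makes the conflict weaker than two mandatory instructions that collide. It does not remove the conflict: on that reading the Grade 2 threshold has no effect for these patients, and nothing in the text says that was intended. Discretion given in one paragraph cannot authorise what another forbids.

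**The specific rule overrides the general one.** This is a reasonable convention, but the protocol does not state it. Apart from the renal rule, the main hold that the lenalidomide guidance sets for non-haematologic toxicity is the one in 4.2.1.3.2. If that paragraph overrode 4.2.1.3, the general prohibition would have little left to govern.

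**The overlap is inferred.** Section 4.2.1.3.2 never uses the word non-haematologic, and the relatedness wording comes from a section headed for haematologic toxicity. That is fair. Overlap is still the natural reading, since platelets and neutrophils have their own tables and what remains plainly includes non-haematologic events.

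**The point could be read too widely.** A reader might infer a three-way contradiction that includes the renal paragraph, or that every patient whose event improves to Grade 2 is caught. The documents support neither. The renal paragraph shares the Grade 1 limit of 4.2.1.3. The exclusions in Steps 3 and 4 also take out patients with Grade 2 at baseline, haematologic and renal events, and patients already at 5 mg. Patients who have reached Grade 1 by the next planned dose are treated alike under both rules.

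**Conclusion.** The inconsistency is real but local. It covers lenalidomide-related, non-haematologic, non-renal Grade 3/4 events that have improved to Grade 2, in patients whose baseline was below Grade 2 and who are not already at the lowest dose level. In that state Section 4.2.1.3.2 allows restart and Section 4.2.1.3 makes it a deviation. The conclusion assumes that the Grade 1 limit means Grade 1 or better, and that the other toxicities of 4.2.1.3.2 include non-haematologic ones.

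The documents do not give the number of patients affected. A reader might infer that adverse event rates, or the stopping rule in Section 7.1.2 on Grade 4 non-haematologic toxicity, would be distorted. That is possible but not shown, since the documents give no frequency of such holds or of recurrence after restart. Nor is the efficacy design touched: the primary endpoint is PFS from transplant in all enrolled subjects, and neither the Simon rule in Section 7.1.3 nor its error rates depend on the restart grade. This is an internal contradiction about treatment conduct that should be corrected. It is not a flaw in the statistical design.

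**What to change.** The sponsor should reconcile Sections 4.2.1.3 and 4.2.1.3.2, and align 4.2.1.3.3 with the result. The revised text should:

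- state one recovery threshold for each toxicity class;
- say for each class whether return to baseline also suffices;
- express the limit as a given grade or lower, to remove the loose wording in 4.2.1.3;
- name the drug to which the renal paragraph applies.

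The same thresholds should then be used in the deviation checks. Which threshold applies is for the sponsor to settle; no position is taken here.

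The cost is a wording amendment to one part of the protocol and a matching entry in the deviation checks. The sample size, the interim rule and the analysis methods need no change.
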